7.5.3.1. Summary Measure

The summary measure is the number and percentage of participants in each of the following derived response categories:

- Strongly prefer Injection with Topical NSAID
- Slightly prefer Injection with Topical NSAID
- No preference
- Slightly prefer Injection with Topical Steroid
- Strongly prefer Injection with Topical Steroid

7.5.3.2. Population of Interest

The Safety population will be used for Cohort 4b crossover analyses.

7.5.3.3. Strategy for Intercurrent (Post-Randomization) Events

A complete case analysis set will be used for the crossover analysis where participants with missing endpoint/variable are excluded. Missing data will not be imputed, regardless of the reason.

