7. DISCONTINUATION OF STUDY INTERVENTION AND PARTICIPANT DISCONTINUATION/WITHDRAWAL

7.1. Discontinuation of Study Intervention

Participants may voluntarily withdraw from the study at any time and for any reason. Site investigators and study staff may withdraw participants before their scheduled termination visit for safety, behavioural, or administrative reasons, or if the participants are unable or unwilling to comply with study procedures. The reasons for withdrawals will be recorded in the participants' study records. If a participant withdraws from the study, he/she may request destruction of any samples taken, and the investigator must document this in the site study records.

During the oral lead-in period, early withdrawal on medical grounds will occur if the participant develops a grade 3 or higher AE that is judged by the investigator to be related

directly to the study product (see [Appendix 3](#) and [Appendix 4](#) for definitions and grading of severity of adverse events), or any AE that is deemed clinically significant by the investigator and is judged by the investigator to be related directly to the study product.

For liver-related stopping criteria, please refer to Section [7.1.1](#).

During the oral lead or injection phase additional pre-specified reasons for discontinuing a participant from the study (or, at minimum, discontinuing administration of study product and continuing safety evaluations) include:

- Pregnancy (please see Section [8.3.5](#))
- Protocol deviation
- Non-compliance
- Participant withdraws consent
- Participant lost to follow-up
- Investigator discretion
- Sponsor discontinues study

During the injection phase of the study reasons for discontinuing study intervention for a participant are outlined below:

- Any participants experiencing a grade 3 or higher AE event prior to the follow-up phase will withdraw from study intervention and enter the follow-up phase if i) the AE is considered related to IP in the opinion of the investigator and sponsor and ii) the investigator and sponsor agree the subject should be withdrawn from study intervention or
- Any participant developing a grade 3 or higher laboratory abnormality (with the exception of asymptomatic Grade 3 or higher cholesterol, triglyceride or CPK increase) prior to the follow-up phase and the investigator and sponsor agree the participant should be withdrawn from study intervention or

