7.5.3. Ordinal Endpoint / Variables

The following ordinal endpoint/variable will be analysed in the crossover analysis comparing preference for topical steroids vs topical NSAIDs for Cohort 4b:

Ordinal Endpoint/Variable

 • For the hypothesis test for evidence of a treatment difference (i.e., p-value), the 5-level ordinal endpoint for Injection Preference from the Preference Questionnaire will be coded as: 
 • -2 (strongly prefer injection 2 compared to injection 1) • -1 (slightly prefer injection 2 compared to injection 1) • 0 (no preference between injection 1 and injection 2) • 1 (slightly prefer injection 1 compared to injection 2) • 2 (strongly prefer injection 1 compared to injection 2)

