No.	Population	GSK Standard/ Example Shell	Title	Programming Notes	Deliverable [Priority]
2.38.	Safety	SAFE_T7b	Event-Level Summary of Duration (Days) at Each Grade – Grading determined according to DAIDS Impact on Social and Function Activities Categories and Occurrence of Other Associated Grade 3 ISRs or Potentially Life-Threatening Consequences – Part 1 Cohort 4h	Repeat for each of the following grouped preferred terms: Erythema/Redness/Induration/Swelling, Erythema/Redness, and Induration/Swelling Injection 1 and Injection 2 periods only. Include pooled treatment groups by dose & route	Cohort 1-5 IA Cohort 1-4, Cohort 1-5, EOS
2.39.	Safety	SAFE_T7c	Subject-Level Summary of Maximum Duration (Days) at Each Grade by Injection Site Reaction Preferred Term – Part 1 & Part 2	Injection 1 and Injection 2 periods only. Include pooled treatment groups by dose & route	Cohort 1-5 IA Cohort 1-4, Cohort 1-5, EOS
2.40.	Safety	SAFE_T7d	Subject-Level Summary of Maximum Duration (Days) at Each Grade – Grading determined according to DAIDS Impact on Social and Function Activities Categories and Occurrence of Other Associated Grade 3 ISRs or Potentially Life-Threatening Consequences – Part 1 Cohort 4h	Repeat for each of the following grouped preferred terms: Erythema/Redness/Induration/Swelling, Erythema/Redness, and Induration/Swelling Injection 1 and Injection 2 periods only. Include pooled treatment groups by dose & route	Cohort 1-5 IA Cohort 1-4, Cohort 1-5, EOS

Safety: Tables					
No.	Population	GSK Standard/ Example Shell	Title	Programming Notes	Deliverable [Priority]
2.41.	Safety	SAFE_T8	Subject- CCI 

 

 

	Injection 1 and Injection 2 periods only.	Cohort 1-4, Cohort 1-5, EOS
Crossover Statistical Analyses for Cohort 4b, including summaries of endpoints for other cohorts					
2.42.	Safety – LA Exposed (Complete Case)	SAFE_XO1	Statistical Analysis for Proportion of Participants with Injection Site Reactions – CCI 

 

 

	CCI 

	Cohort 1-5, EOS
2.43.	Safety – LA Exposed (Complete Case)	SAFE_XO2	CCI 

		Cohort 1-5, EOS
2.44.	Safety – LA Exposed (Complete Case)	SAFE_XO3			Cohort 1-5, EOS
2.45.	Safety – LA Exposed (Complete Case)	PIN_XO1			Cohort 1-5, EOS
2.46.	Safety – LA Exposed (Complete Case)	PIN_XO2			Cohort 1-5, EOS

Safety: Tables					
No.	Population	GSK Standard/ Example Shell	Title	Programming Notes	Deliverable [Priority]

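### The Cohort 4b injection site reaction crossover tables use complete cases, so some severe Injection 1 reactions can drop out because of the outcome being compared; a supportive analysis should keep them

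*SAP*

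**What the plan says.** Cohort 4b randomises 24 participants, 12 per sequence, to a topical NSAID with one injection and a topical steroid with the other (Protocol 4.1.1 and Section 8).

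- **Missing-data rule.** SAP 7.5.3.3 states "A complete case analysis set will be used for the crossover analysis where participants with missing endpoint/variable are excluded" and adds "Missing data will not be imputed, regardless of the reason". It sits under SAP 7.5.3, which is about preference: "The following ordinal endpoint/variable will be analysed in the crossover analysis comparing preference for topical steroids vs topical NSAIDs for Cohort 4b". The preceding parts of SAP 7.5 are redacted.
- **Display list (SAP 10.10.5).** Table 2.42 is titled "Statistical Analysis for Proportion of Participants with Injection Site Reactions" and its population reads "Safety – LA Exposed (Complete Case". Tables 2.43 to 2.48 carry the same label, with their titles redacted.
- **Population in the text.** SAP 7.5.3.2 says "The Safety population will be used for Cohort 4b crossover analyses".
- **Stopping injections.** Protocol 7.1 says "Any participants experiencing a grade 3 or higher AE event prior to the follow-up phase will withdraw from study intervention". Two conditions follow: "i) the AE is considered related to IP in the opinion of the investigator and sponsor", and agreement between investigator and sponsor that the person should stop. Someone who stops in the injection phase is still followed, so the Injection 1 reactions are recorded.
- **SAP default.** SAP 10.7.1 puts available planned data from withdrawn participants into summaries unless another rule is given.

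**The concern.** A two-period comparison restricted to people with both periods is safe when the second period is missing for unrelated reasons. Here one route to a missing Injection 2 is a severe reaction to Injection 1, which is the kind of outcome the crossover compares between topicals. If such people leave the analysis set, the comparison describes those who went on to a second injection. The reported proportions by topical are then too low, and the risk difference for severe reactions moves toward zero.

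The quoted rule is written for preference, where it is unavoidable because preference needs two injections. It reaches reactions through the population label on Table 2.42. SAP 10.7.2.1 also shows that the crossover endpoints are wider than preference, because it gives a date rule for the duration of ongoing events in Section 7.5. No analysis that keeps one-period data is visible for the crossover.

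**Working it through.** **The plan's own figure.** Protocol 10.2 gives 93 evaluable participants in Part 1: 5 × 15 + 18 = 93, which agrees. For Cohort 4b, 18/24 = 75%, so a 25% loss is allowed. Cohorts planned at 20 with 15 evaluable allow the same (15/20 = 75%). This is a general allowance, not evidence of reaction-driven loss. The Cohort 4b sample-size rationale is redacted and cannot be derived.

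**Assumptions (none is in the documents).** The endpoint is a Grade 3 or higher ISR. The true proportions on the two topicals are pA and pB, and p11 is the probability of reacting on both. The probability that a Grade 3 reaction at Injection 1 leads to no Injection 2 is w, the same for both topicals. There is no period effect, sequences are equal in size, and one-period participants are excluded.

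**Formula,** taking each sequence as size 1:

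- Retained: (1 − w·pA) + (1 − w·pB) = 2 − w(pA + pB)
- A events retained: pA(1 − w) + (pA − w·p11) = pA(2 − w) − w·p11
- B events retained: pB(2 − w) − w·p11
- Complete-case difference: (pA − pB)(2 − w) / [2 − w(pA + pB)]

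The within-person term p11 cancels from the difference. With pA = 0.20 and pB = 0.10 the difference is (0.2 − 0.1w)/(2 − 0.3w), against a true 0.10.

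| w | Retained of 24, 12(2 − 0.3w) | Difference | Shrinkage | Proportions, independent (p11 = 0.02) | Proportions, latent correlation 0.5 |
|---|---|---|---|---|---|
| 0.25 | 23.1 | 0.175/1.925 = 0.091 | 9% | 17.9% vs 8.8% | 17.5% vs 8.4% |
| 0.50 | 22.2 | 0.150/1.850 = 0.081 | 19% | 15.7% vs 7.6% | 14.8% vs 6.7% |
| 1.00 | 20.4 | 0.100/1.700 = 0.059 | 41% | 10.6% vs 4.7% | 8.7% vs 2.9% |

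**Other rates.** For 30% vs 10%, the true 0.200 becomes 0.184, 0.167 and 0.125. For 40% vs 20%, it becomes 0.189, 0.176 and 0.143. With equal rates the difference stays at 0.

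**Share of events lost.** Only Injection 1 events can be lost, and they are half of the expected total. The share is w/2: 12.5%, 25% and 50%.

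**Discordant pairs.** A-only pairs retained are (pA − p11)(2 − w), and B-only pairs are (pB − p11)(2 − w). The factor cancels, so the ratio is unaffected: with p11 = 0.02 it is 0.18/0.08 = 2.25 at every w.

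**Against sampling error.** With 24 complete pairs and p11 = 0.02, the standard error of the difference is √[(0.20 + 0.10 − 0.04 − 0.01)/24] = √(0.25/24) = 0.102. The shifts of 0.9, 1.9 and 4.1 points are all below half of that. An Injection 1 comparison between sequences (12 vs 12) keeps the true 0.10, but its standard error is √[(0.16 + 0.09)/12] = 0.144.

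**Limit of the formula.** The difference shrinks only while pA + pB is below 1. It should not be carried over to an any-grade endpoint. Protocol 2.3.1 reports that most people given the 200 mg/mL formulation have some ISR, and only the Grade 3 minority would be exposed to this exclusion.

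**The case against.** The strongest reply is that the ISR method is not visible. The quoted rule belongs to preference, the Table 2.42 label does not say what counts as a missing reaction endpoint, and a redacted section could hold a sensitivity analysis. This stands in part: the loss of Injection 1 results is a natural reading of complete case in a two-period design, not a stated rule.

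A reader might infer more than the documents support:

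- **That the protocol withholds Injection 2 after any Grade 3 reaction.** It does not. Relatedness and agreement by investigator and sponsor are both required.
- **That the worst reactions to each topical are removed.** A Grade 3 reaction at Injection 2, or at Injection 1 without withdrawal, stays in.
- **That these reactions vanish from the report.** Tables 2.2 and 2.4 summarise ISRs in injection-exposed participants and are not complete-case, and reasons for stopping appear in Table 1.5 and Listings 4 and 22. These keep the events. SAP 7.1 pools Cohort 4b injection data across the topicals in its period summary; a further breakdown may be redacted.
- **That this is the main question of Cohort 4b.** The SAP amendment table calls the crossover analysis exploratory, and no formal hypothesis is tested in the study.

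It is also fair that no Grade 3 crossover endpoint is visible, that the protocol describes ISRs with the 200 mg/mL formulation as generally Grade 1 or 2, and that the shift is smaller than sampling error. If the redacted test uses discordant pairs, its odds ratio is unbiased in this model. The by-topical proportions and the risk difference are still affected.

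**Conclusion.** The concern holds in a limited form. On the natural reading, the complete-case set for the ISR crossover endpoints can exclude Injection 1 severe reactions because of the outcome being compared, although those reactions are recorded. At assumed Grade 3 rates of 20% and 10%, the risk difference is understated by about 9%, 19% or 41% as w goes from 25% to 50% to 100%. The last value treats a discretionary rule as automatic and is an upper bound.

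The absolute shift, 0.9 to 4.1 points, is modest beside a standard error of about 10 points. It is smaller still if Grade 3 reactions or withdrawals are rare, or if the endpoint counts all grades. Rates, w and the correlation are all assumptions. The result calls for a supportive analysis, not replacement of the planned test. The mismatch between SAP 7.5.3.2 and the display list is real but editorial.

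**What to change.** In SAP 7.5 and the display list:

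1. Keep the planned complete-case test.
2. For the ISR crossover endpoints, add a supportive analysis of all LA-exposed Cohort 4b participants that retains Injection 1 data from those without Injection 2. Use a mixed model with treatment and period, or a between-sequence comparison at Injection 1. Present ISR proportions by topical over all injections given.
3. Report the number excluded from the complete-case set by sequence and reason.
4. Leave preference (Table 2.48) complete-case.
5. Make the population in SAP 7.5.3.2 agree with the display list.

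The cost is SAP wording and one extra exploratory model, with no effect on trial conduct. The model may not converge with 24 participants. The Injection 1 comparison is then the fallback, at the loss of precision shown above.

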7.5.3.4. Statistical Analyses / Methods

The number and percentage of participants with preference corresponding to each of the 5 ordinal outcomes will be summarized. The number and percentage of participants reporting each statement supporting their preferences as collected in the eCRF will also be summarized.

Details for the planned display are provided in [Appendix 10: List of Data Displays](#) and will be based on GSK Data Standards and statistical principles.

Statistical Methodology Specification

 • Extended Mantel-Haenszel test using the SAS Proc Freq procedure. • Implementation notes/pseudo code: <pre>proc freq; tables sequence*outcome/measures nocol norow nopct; exact mhchi; run;</pre>
Results Presentation

 • Exact two-sided p-value from extended Mantel-Haenszel test

8. PHARMACOKINETIC ANALYSES

8.1. Primary Pharmacokinetic Analyses

8.1.1. Endpoint / Variables

8.1.1.1. Drug Concentration Measures

Refer to [Appendix 5: Data Display Standards & Handling Conventions](#) (Section 10.5.3 Reporting Standards for Pharmacokinetic). Plasma concentrations of CAB will be measured and reported.

8.1.1.2. Derived Pharmacokinetic Parameters

Pharmacokinetic parameters will be calculated by standard non-compartmental analysis according to current working practices and using the currently supported version of WinNonlin (8.0 or higher). All calculations of non-compartmental parameters will be based on actual sampling times. Pharmacokinetic parameters listed will be determined from the plasma concentration-time data from OLI and Injection phases, as data permit.

Parameter	Parameter Description	OLI Phase	Injection Phase
C _{max}	Maximum observed plasma concentration determined directly from the concentration-time data.	Day 1	For Injection 1 and 2 in Part 1 and Part 2
C _{max} /D	Dose normalized C _{max} , calculated as C _{max} /Dose	Day 1	For Injection 1 and 2 in Part 1 and Part 2
t _{max}	Time of C _{max} determined directly from the concentration-time data.	Day 1	For Injection 1 and 2 in Part 1 and Part 2
AUC(0-t)	Area under the concentration time curve from time zero to last quantifiable time point calculated using the linear trapezoidal rule for each incremental trapezoid and the log trapezoidal rule for each decremental trapezoid.	Day 1	For Injection 1 & 2 in Part 1 and Part 2
AUC(0-t)/D	Dose normalized AUC(0-t), calculated as AUC(0-t)/Dose	Day 1	For Injection 1 & 2 in Part 1 and Part 2
AUC(0-τ)	Area under the concentration time curve from time zero to tau time point calculated using the linear trapezoidal rule for each incremental trapezoid and the log trapezoidal rule for each decremental trapezoid. Tau=24 hours for OLI Day 1 Tau is 4 weeks for Cohort 1-4, 4b and 4h Tau is 12 weeks for cohort 5	Day 1	For Injection 1 & 2 in Part 1 and Part 2
AUC(0-τ)/D	Dose normalized AUC(0-τ) calculated as AUC(0-τ)/Dose	Day 1	For Injection 1 & 2 in Part 1 and Part 2

Parameter	Parameter Description	OLI Phase	Injection Phase
AUC(0-4) Cohort 5 only	Area under the concentration time curve from time zero to Week 4 calculated using the linear trapezoidal rule for each incremental trapezoid and the log trapezoidal rule for each decremental trapezoid.	NA	Injection 1 Part 2 (Cohort 5) (this parameter is used in the dose proportionality analysis).
AUC(0-∞)	Area under the concentration time curve from time zero to infinity	NA	For Injection 1 (Cohort 4h) & 2 in Part 1 and Part 2
AUC(0-∞)/D	Dose normalized AUC(0-∞), calculated as AUC(0-∞)/Dose	NA	For Injection 1 (Cohort 4h) & 2 in Part 1 and Part 2
C _τ	Trough concentrations (C _τ) Tau=24 hours for OLI Day 29 Tau is 4 weeks for Inj. Phase in Cohort 1-4, 4b, and 4h Tau is 12 weeks for Inj. Phase in cohort 5.	Day 29	For Injection 1 & 2 in Part 1 and Part 2
C _τ /D	Trough concentrations (C _τ)/Dose Tau=24 hours for OLI Day 29 Tau is 4 weeks for Inj. Phase in Cohort 1-4, 4b, and 4h Tau is 12 weeks for Inj. Phase in cohort 5.	Day 29	For Injection 1 & 2 in Part 1 and Part 2
C4 Cohort 5 only	Trough concentrations on Week 4	NA	For Injection 1 & 2 in Part 2
C24	Trough Concentrations on Day 2 (24 hour)	Day 1	
t _{1/2}	Terminal absorption elimination half-life will be calculated as: t _{1/2} = ln2 / KALA	NA	For Injection 1 (Cohort 4h) & 2 in Part 1 and Part 2.
KALA	Terminal absorption elimination rate constant, Long-acting	NA	For Injection 1 (Cohort 4h) & 2 in Part 1 and Part 2

NOTES:

- Additional parameters may be included as required.
- In addition to the PK parameters calculated based on the observed concentrations for the 2 participants from Cohort 3 who received a CAB400 - Inj. 1 400 mg IM Lateral Thigh. PK parameters adjusted to a 600 mg dose will be calculated for these participants as well. The adjustment will be performed using a 50% increase of the plasma PK parameters.

